SparkRx group: The SparkRx mobile program will be 5 weeks in duration and self-guided. The five modules in this program are each expected to take around 60 minutes to complete. Modules do not need to be completed in a single session but can be completed over the course of several days. Emergency resources for participants experiencing thoughts of suicide or self-harm will be available in the app. While participants can progress through the programs at their own pace, participants will be instructed to complete one module in the mobile app per week, and to complete the program within the 5-week intervention period. Participants will be prompted to complete weekly PHQ-8 and PSC in the mobile application. App notifications, text (SMS) and/or email messages may be sent to participants to encourage them to complete the weekly assessments (i.e., PHQ-8 and PSC). To encourage participants to engage with the app, automated app notifications will also be sent. For participants under 18 years of age, legal guardians may receive email and/or text notifications to complete proxy PHQ-8 and PSC assessments in the secure web portal.

eUC group: Participants will download a mobile app that contains no content, but that provides access to in-app weekly PHQ-8 and PSC assessments.

All participants will receive notifications (app notifications and SMS and/or email) to complete the PHQ-8 and PSC). For participants under 18 years of age, legal guardians may receive email and/or text notifications to complete proxy PHQ-8 and PSC assessments in the secure web portal .

Post-intervention period

After the 5-week intervention period, all participants will be sent links via email and/or text to complete post-intervention self-report questionnaires in the secure web portal. Participants may receive automated email and text reminders to complete the post-intervention questionnaires. A study coordinator may also contact participants (and legal guardians) who have not completed post-intervention questionnaires before they reach a 2 week deadline.

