One month after the end of the intervention period, participants will be prompted to complete self-report questionnaires to evaluate sustained effects of the intervention on relevant outcomes. Participants may receive automated email and text reminders to complete the questionnaires. A study coordinator may contact participants (and legal guardians) who have not completed follow-up questionnaires before they reach a 2 week deadline. Participants who do not complete the one-month follow-up questionnaires within 2 weeks will be considered lost to follow-up.

If a participant chooses to withdraw from the study at any point or the participant is dropped from the study during the intervention period (5 weeks), access to the web portal and mobile app will be restricted at that time; otherwise access to the mobile app will be restricted at the end of week 5 and access to the web portal will be restricted after 1-month follow-up assessments have been completed or the participant is deemed lost to follow-up.

All relevant FDA requirements for the conduct of clinical trials will be followed, including registration on clinicaltrials.gov. Email and other notification templates are provided in Appendix 6.

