3.4 Assessments

The following Prescreening, Baseline, post-intervention, and follow-up assessments will be completed via secure web portal. Weekly participant assessments (PHQ-8, PSC) will be completed in the mobile app. Weekly legal guardian assessments (PHQ-8, PSC proxies) will be completed via the secure web portal. All assessments are provided in Appendix 1, with the exception of the Prescreening Questionnaire (Appendix 3).

Table 1. Schedule of Assessments					
	Eligibility Screening	Baseline	Weekly during intervention period	Post-intervention	1-month follow-up (4 weeks post intervention)
Prescreening Questionnaire	X (if used)				
Patient Health Questionnaire (PHQ-8)	X		X	X	X
Medication Use Screener	X				
Baseline Questionnaire		X			
Baseline Questionnaire, legal guardian proxy*		X			
Patient Health Questionnaire (PHQ-8, legal guardian proxy*)		X	X	X	X
Behavioral Activation for Depression Scale - short form (BADS)		X		X	X
Generalized Anxiety Disorder (GAD-7)		X		X	X
Pediatric Quality of Life Enjoyment & Satisfaction Questionnaire (PQ-LES-Q)		X		X	X
Pediatric Quality of Life Enjoyment & Satisfaction Questionnaire (PQ-LES-Q, legal guardian proxy*)		X		X	X
Participant Symptom Check (PSC)			X	X	X

Participant Symptom Check (PSC, legal guardian proxy*)			X	X	X
Post-Intervention Questionnaire				X	
Post-Intervention Questionnaire, legal guardian*				X	
Systems Usability Scale (SUS)				X	
User Engagement Scale (UES-SF)				X	
1 month follow-up Questionnaire					X
1 month follow-up Questionnaire, legal guardian*					X
Absenteeism Questionnaire		X		X	X
Healthcare Utilization Questionnaire		X		X	X
Absenteeism Questionnaire, legal guardian*		X		X	X
Healthcare Utilization Questionnaire, legal guardian*		X		X	X

* Only administered when participants are under 18 years of age

Description of Assessments

- The **Prescreening Questionnaire** is administered to potential participants on the study website landing page and assesses whether or not participants are preliminarily eligible to participate based on yes/no/unsure responses to clustered sets of eligibility criteria (Appendix 3).

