4.7 Data Analysis

Detailed statistical analysis plans (SAP) will be developed prior to completion of primary outcome data collection. Prior to analysis, study population details including the number randomized to each study arm and lost to follow-up will be described. Baseline participant characteristics will be summarized for the SparkRx and eUC arms as means, standard deviations, medians, 25th and 75th percentiles for continuous variables, and as counts and percentages for categorical variables. Differences in baseline characteristics between the groups will be explored using tabular and visual displays, as appropriate, and appropriate statistical tests (e.g., independent sample t-tests for continuous variables, chi-square tests for categorical variables).

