4.7.1 General Approach

Analysis Populations: All analyses will be completed in line with the intention-to-treat (ITT) principle, where all participants will be included in the analyses according to their assigned study arm at baseline, regardless of adherence to study protocol. Per-protocol analyses will also be conducted to estimate treatment effects for participants who adhered to the protocol, and will include individuals who completed the Baseline and post-intervention PHQ-8 assessments and, for participants in the SparkRx group, met a minimum engagement threshold of completing two modules.

Descriptive Statistics: For descriptive statistics, the following will be reported:

Continuous data: n, mean, standard deviation, median and interquartile range, minimum and maximum

Categorical: n/N and percentage of total per arm

Missing Data: We do not anticipate missing data for the stratification variables, which will be included as covariates in the analysis models. Ongoing efforts will be made to reduce the amount of missing data for all outcomes. Despite these efforts, missing data for primary, secondary, and tertiary/exploratory outcomes are likely. Data missing at random (MAR) on dependent variables are easily handled in repeated measures mixed models so no imputation will be needed. For all other statistical analyses described below and missing data on covariates (or independent variables) in models, multiple imputation will be used if at least 5% of data points are missing for a given covariate or variable. Case analysis or single imputation methods may also be used and a specific approach for imputation will be selected based on key attributes of the obtained data, including percent missing and whether data are missing at random. We will compare the results obtained with and without imputation. Sensitivity analyses will be used to assess the impact of potential deviations from the MAR assumption on the study findings.

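### Participants whom the study drops before week 5 lose both described PHQ-8 routes, which adds avoidable missing outcomes; the likely effect is small and the remedy inexpensive

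*Combined protocol and SAP*

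**What the plan says.** Section 3.1 (Procedure) closes access at once for anyone who withdraws or is "dropped from the study during the intervention period (5 weeks), access to the web portal and mobile app will be restricted at that time". For everyone else the app closes at the end of week 5 and the portal after the 1-month follow-up.

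Both places where a participant's PHQ-8 is recorded after randomisation fall under that closure:

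- Section 3.4: "Weekly participant assessments (PHQ-8, PSC) will be completed in the mobile app".
- Section 3.1, post-intervention period: "all participants will be sent links via email and/or text to complete post-intervention self-report questionnaires in the secure web portal".

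Section 3.1 mentions coordinator contact only as a reminder to complete outstanding questionnaires. No telephone, paper or interview PHQ-8 is described.

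Section 4.7.1 sets the analysis aim: "all participants will be included in the analyses according to their assigned study arm at baseline, regardless of adherence to study protocol". It adds: "Ongoing efforts will be made to reduce the amount of missing data for all outcomes". Missing outcomes in the mixed model are handled under missing at random (MAR). For other analyses, "multiple imputation will be used if at least 5% of data points are missing for a given covariate or variable", although case analysis or single imputation is also allowed. It also promises: "Sensitivity analyses will be used to assess the impact of potential deviations from the MAR assumption on the study findings".

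Removal by the study after randomisation is foreseen for administrative reasons (section 3.1: location or healthcare provider cannot be confirmed) and for clinical ones (section 4.8: decision after a serious AE or UADE; section 4.8.1: high suicide risk; section 7.3: the participant's best interest).

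**The concern.** The loss is created by a rule of the study. A participant dropped in week 2 may be willing to answer the week-5 questionnaire, but has no described means of doing so. Analysis cannot recover a score that was never collected.

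The clinical grounds for removal are plausibly related to the PHQ-8 itself, so MAR is least secure in this group. Removal could also differ by arm: in-app free text is reviewed for safety in SparkRx only (sections 3.2 and 4.5), while eUC has no such text (section 3.3). Against that, both arms have the weekly PHQ-8, free text in the weekly symptom check, and deterioration alerts.

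The primary model is partly protected, because scores recorded before removal stay in it. Response, remission and the 5-point reduction are less protected. Section 4.7.3 compares them by chi-square test at post-intervention, and they use no weekly scores unless imputation brings them in.

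**Working it through.** **The plan's own figures (section 4.6).** For d = 0.4, two-sided 0.05 and 80% power, the t-test needs 99.1 per arm, rounded up to 100 (power 80.4%). For attrition, 200 × 1.10 = 220, while 200/0.90 = 222.2. With 220 enrolled and 10% lost, 220 × 0.90 / 2 = 99 per arm remain, with power 79.97%. The stated size reproduces. No separate rate is given for participants dropped by the study.

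**Power.** If removals are already inside the 10%, nothing changes. If they come on top of it, t-test power falls from 80.0% to 79.1% at 2% removed and to 77.7% at 5% removed.

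**Assumptions for bias (none is in the documents).** Removed: 5% of SparkRx and 2% of eUC. With 110 per arm, 0.05 × 110 = 5.5 and 0.02 × 110 = 2.2, in total 7.7 of 220 (3.5%). Removed participants average 1 SD worse than their arm.

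**Mixed model.** Simulation under no treatment effect, 110 per arm, baseline plus five weekly scores with SD 1, baseline slope 0.6, residual correlation AR(1) 0.8 or compound symmetry 0.5. The model follows section 4.7.2 with linear time, arm, time by arm and baseline; antidepressant status was not simulated and the covariance was taken as known. The contrast is at week 5, with 6,000 runs and Monte Carlo SE 0.0012 to 0.0014. Removal probability is p × exp(s − 0.5), so removed participants average +1 SD on s. Negative values favour SparkRx.

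| Removal follows | AR(1), after week 1 | AR(1), after week 3 | CS, after week 1 | CS, after week 3 |
|---|---|---|---|---|
| unobserved final score | −0.0170 | −0.0124 | −0.0130 | −0.0071 |
| last observed and final score equally | −0.0075 | −0.0038 | −0.0077 | −0.0066 |

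If removal follows the last observed score alone, the bias is −0.0001 to +0.0006. Type I error was 4.3% to 5.7% (Monte Carlo SE 0.3 points), so no inflation was detectable. Equal rates (3.5% in both arms) give −0.0003 to +0.0016. Reversed rates (2% and 5%, after week 3) give +0.0044 to +0.0095, against SparkRx.

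The largest value, 0.017 SD, is 0.017/0.4 = 4% of the design effect, or 0.017 × 5 = 0.09 PHQ-8 points at an assumed SD of 5. A cruder bound that gives no credit to scores before removal is (0.05 − 0.02) × 1 SD = 0.03 SD.

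**Responder outcomes, upper illustration.** Assume true response of 40% and 25% (15.0 points), every removed participant a non-responder, and complete-case analysis:

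- 5% and 2% removed: 0.40/0.95 − 0.25/0.98 = 16.6 points
- 3.5% and 3.5%: 0.40/0.965 − 0.25/0.965 = 15.5 points
- 2% and 5%: 0.40/0.98 − 0.25/0.95 = 14.5 points

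Removals of 3.5% alone would not reach the 5% trigger for multiple imputation. The anticipated 10% attrition would, and imputation using the weekly scores could bring these figures closer to 15.0.

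**The case against.** The strongest reply is that the numbers are small and rest on inputs chosen high. The 5% and 2% split is assumed, every removed participant is taken as 1 SD worse although some removals are administrative, and the responder illustration ignores the imputation the plan provides for. Attrition is already budgeted and MAR sensitivity analyses are promised. On detail, section 4.7 says: "Detailed statistical analysis plans (SAP) will be developed prior to completion of primary outcome data collection". All of this stands. It limits the priority, and the absence of a named method for data not missing at random is not a gap at this stage.

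A second reply is that the loss is not absolute. The extent of the restriction is not defined, the safety protocol and the consent pages are not in the available text, and someone dropped late in week 5 may already have given that week's in-app score. This also stands, which is why the claim is that such participants will normally lack the outcome.

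Three stronger readings are tempting but unsupported:

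- A reader might infer that section 3.1 contradicts itself, or contradicts intention to treat, because all participants are to be sent links and analysed. The closure reads naturally as a specific exception, and the ITT statement governs analysis by assigned arm; it does not promise follow-up after removal.
- A reader might infer that the result is tilted towards SparkRx. That needs unequal removal in one particular direction, and the documents give no rate in either arm.
- A reader might infer that continued collection would let MAR be tested, or would remove most of the bias. Even if 60% of the assumed removals replied, that is 0.6 × 5.5 = 3.3 in SparkRx and 0.6 × 2.2 = 1.3 in eUC. Some removed participants could not be approached at all. If half could be and 60% of those replied (both assumed), 30% would supply a score; a separate 4,000-run check gave a remaining bias of 0.005 to 0.015 SD, against 0.009 to 0.015 SD with no change.

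**Conclusion.** The point holds as a modest design weakness. With both described routes closed, a randomised participant dropped by the study before week 5 will normally have no post-intervention primary or responder outcome. The missing data are partly avoidable and partly related to clinical state.

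Under the assumed 5% and 2% removal with a 1 SD difference, bias in the primary model is at most about 0.02 SD (0.03 SD on the cruder bound). It is about zero with equal rates, and its direction is unknown. The responder outcomes are somewhat more exposed, but less than the shift from 15.0 to 16.6 points if multiple imputation is used. Confidence is medium, because the removal rate is unknown and the wording on restriction can be read in more than one way. The case for change rests on its low cost and on the fact that uncollected scores cannot be recovered, not on the size of the bias.

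**What to change.** In section 3.1, separate the end of app use from the end of outcome collection, and state whether outcome collection ends when a participant is dropped. Keep the existing portal's post-intervention and 1-month questionnaires open for dropped participants who have not withdrawn consent to data collection and for whom the sponsor's clinicians and the IRB judge that the study's safety procedures can still be applied. Whether someone removed for clinical or safety reasons may be contacted is for those clinicians and the IRB to decide.

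Reconcile sections 3.1, 4.7.1, 4.8, 4.8.1 and 7.3 on this point, and report removals by arm and reason. No removal or clinical rule is proposed or changed.

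The cost is protocol, consent and IRB wording, a portal permission setting, and safety review of the extra responses. The downside is limited reach: at most about 8 of 220 under the assumed rates, fewer once those who cannot be followed safely are left out, and with incomplete response. The gain is slightly less missing data. This is a low-priority improvement.

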3.2 Description of the Limbix SparkRx Program

The SparkRx program is a 5-week program divided into 5 levels intended to be completed weekly. A character called 'Limbot' is used as a guide. Limbot encourages the user in completing the behavioral activation program and provides personal examples of how they have undertaken behavioral activation therapy. Participants are instructed to complete a weekly PHQ-8 assessment and PSC in the mobile app. Tasks in the mobile app

progress in a linear fashion -- i.e., each task must be completed to progress to the next task. Certain on-demand resources can be accessed in the app at any time, including crisis resources. Text entries that match a database of concerning words/phrases will trigger an automated pop-up suggesting participants visit the in-app crisis resources if they need additional support. Study staff will monitor participants' freeform text, symptom deterioration, pop-up alerts, and questionnaire data for safety.

3.3 Description of assessment-enhanced Usual Care (eUC)

UC is based on a stepped care model for treatment for symptoms of depression. It can include any of the following: active monitoring of depressive symptoms and suicidality, supportive counseling by a healthcare provider, psychosocial support interventions, collaborative care (e.g. facilitation of parental and patient self-management, referral for peer support or other community or school-based behavioral health programs), psychoeducation, complementary and alternative medicine approaches, psychotherapy (e.g. behavioral treatment, interpersonal therapy, cognitive behavioral therapy), pharmacotherapy for mood problems, visit to a primary care provider, behavioral or mental health specialist or therapist, counselor or coach for mood disorder. For purposes of this study, UC will be enhanced by prompting participants to complete weekly PHQ-8 and PSC assessments in a mobile app. Study staff will monitor participants' symptom deterioration and questionnaire data for safety.

3.4 Assessments

The following Prescreening, Baseline, post-intervention, and follow-up assessments will be completed via secure web portal. Weekly participant assessments (PHQ-8, PSC) will be completed in the mobile app. Weekly legal guardian assessments (PHQ-8, PSC proxies) will be completed via the secure web portal. All assessments are provided in Appendix 1, with the exception of the Prescreening Questionnaire (Appendix 3).

Table 1. Schedule of Assessments					
	Eligibility Screening	Baseline	Weekly during intervention period	Post-intervention	1-month follow-up (4 weeks post intervention)
Prescreening Questionnaire	X (if used)				
Patient Health Questionnaire (PHQ-8)	X		X	X	X
Medication Use Screener	X				
Baseline Questionnaire		X			
Baseline Questionnaire, legal guardian proxy*		X			
Patient Health Questionnaire (PHQ-8, legal guardian proxy*)		X	X	X	X
Behavioral Activation for Depression Scale - short form (BADS)		X		X	X
Generalized Anxiety Disorder (GAD-7)		X		X	X
Pediatric Quality of Life Enjoyment & Satisfaction Questionnaire (PQ-LES-Q)		X		X	X
Pediatric Quality of Life Enjoyment & Satisfaction Questionnaire (PQ-LES-Q, legal guardian proxy*)		X		X	X
Participant Symptom Check (PSC)			X	X	X

Participant Symptom Check (PSC, legal guardian proxy*)			X	X	X
Post-Intervention Questionnaire				X	
Post-Intervention Questionnaire, legal guardian*				X	
Systems Usability Scale (SUS)				X	
User Engagement Scale (UES-SF)				X	
1 month follow-up Questionnaire					X
1 month follow-up Questionnaire, legal guardian*					X
Absenteeism Questionnaire		X		X	X
Healthcare Utilization Questionnaire		X		X	X
Absenteeism Questionnaire, legal guardian*		X		X	X
Healthcare Utilization Questionnaire, legal guardian*		X		X	X

* Only administered when participants are under 18 years of age

Description of Assessments

- The **Prescreening Questionnaire** is administered to potential participants on the study website landing page and assesses whether or not participants are preliminarily eligible to participate based on yes/no/unsure responses to clustered sets of eligibility criteria (Appendix 3).
- The **Patient Health Questionnaire (PHQ-8) Participant and Legal Guardian Proxy** is an 8-item participant-report measure for screening for depression and for establishing depression severity¹⁰⁰. The total score ranges from 0-24, with a higher score indicating greater depression symptom severity. For participants under 18, a legal guardian proxy version of the PHQ-8 will be administered to legal guardians. Clinically significant improvement is defined as a reduction in assessment score ≥ 5 ¹⁰¹. Intervention response is defined as 50% reduction in symptoms from pre- to post-intervention, and remission is defined as a score < 5 following intervention¹⁰².
- **Medication Use Screener** is a single-item screening form that asks participants to report whether or not (yes/no) they are currently taking psychotropic medication for the treatment of depression or symptoms of depression.
- **7 item Generalized Anxiety Disorder scale (GAD-7)**. The GAD-7 is a validated 7-item participant-reported assessment for generalized anxiety disorder¹⁰³. We will evaluate changes in anxiety symptoms given the high comorbidity between anxiety and depression. The total score ranges from 0-21, with a higher score indicating greater anxiety symptom severity.
- **Pediatric Quality of Life Enjoyment & Satisfaction Questionnaire (PQ-LES-Q) Participant & Legal Guardian**: A 15-item participant-reported self-administered questionnaire that captures life satisfaction over the past week¹⁰⁴. Each question is rated on a 5-point scale from 1 (Very Poor) to 5 (Very Good). The first 14 items are summed to form a total score ranging from 14-84, with higher scores indicating higher quality of life. The 15th item ("Overall, how has your life been?") is a stand-alone item. For participants under 18, a legal guardian proxy version of the PQ-LES-Q will also be administered to legal guardians.
- **Participant Symptom Check (Participant and Legal Guardian)**. Assesses legal guardian- and participant- reported negative symptoms and changes in treatment since the last check-in, using multiple choice and free-form text responses.
- **Behavioral Activation for Depression Scale - Short Form (BADS)**. The BADS¹⁰⁵ consists of 9 participant-reported questions assessing behavioral activation and avoidance over the previous week, each rated on a 7-point scale ranging from 0 (not at all) to 6 (completely). This form can be used to track behaviors hypothesized to underlie depression and specifically targeted for change by behavioral activation. It examines changes in the following areas: activation, avoidance/rumination, work/school impairment, and social impairment. The total score ranges from 0 to 54, with higher scores indicating higher activation.
- **Baseline Questionnaire (Participant and Legal Guardian)**. This participant- and legal guardian-reported questionnaire includes participant age, sex, gender, socio-economic status, medical

history, and medications.

- **Post-Intervention Questionnaire (Participant and Legal Guardian).** This participant- and legal guardian-reported questionnaire assesses feedback on the mobile app.
- **System Usability Scale (SUS).** The SUS¹⁰⁶ is a participant-reported scale that provides a quick, reliable tool for measuring the usability of the mobile app. The SUS consists of a 10-item questionnaire with five response options for respondents, ranging from Strongly Agree to Strongly Disagree. The total score ranges from 0-100, with higher scores indicating greater usability.
- **User Engagement Scale - Short Form (UES-SF).** The UES-SF¹⁰⁷ is a participant-reported, statistically reliable measure of self-reported user engagement that is tailored to the specific device being tested (i.e., the study app). The form has 12 items and uses a 5-point Likert scale. There are 4 subscales: Aesthetic appeal, focused attention, perceived usability, and reward. Each subscale score ranges from 1-5, with higher scores indicating higher levels of each scale. The total score also ranges from 1-5, with higher scores indicating more engagement.
- **One month follow-up Questionnaire (Participant and Legal Guardian).** This participant- and legal guardian-reported questionnaire assesses feedback on the mobile app.
- **Absenteeism Questionnaire (Participant and Legal Guardian)** This participant- and legal guardian-reported questionnaire assesses missed time at work and/or school attributable to the participant's mental health condition over the past 4 weeks.
- **Healthcare Utilization Questionnaire (Participant and Legal Guardian)** This brief participant- and legal guardian-reported questionnaire assesses use of healthcare resources over the past 4 weeks.

4. Data Analysis and Data Monitoring

